2.3.1 Patient disposition

Enrollment by country will be summarized for all screened patients and also by cohort using the FAS and repeated on the mFAS as appropriate. The number (%) of treated patients included in the FAS will be presented by cohort. The number (%) of screened and not-treated patients and the reasons for screening failure will also be displayed. The number (%) of patients in the FAS who are still on treatment, who discontinued the study phases and the reason for discontinuation will be presented by cohort.

The following summaries will be provided (with % based on the total number of FAS patients):

- Number (%) of patients who are still on-treatment (based on the 'End of Treatment Phase' page not completed);
- Number (%) of patients who discontinued the study treatment phase (based on the 'End of Treatment Phase' page)
- Primary reason for study treatment phase discontinuation (based on the 'End of Treatment Phase' page)
- Number (%) of patients who have entered the post-treatment follow-up (based on the 'End of Treatment Phase' page);
- Number (%) of patients who have discontinued from the post-treatment follow-up (based on the Study Evaluation Completion/ End of Post-treatment follow-up page);
- Reasons for discontinuation from the post-treatment follow-up (based on Study Evaluation Completion/ End of Post-treatment follow-up page);

Note: post-treatment follow-up for patient disposition only refers to efficacy follow-up.

2.3.2 Patient disposition in Extension Phase

Patient disposition in Extension Phase will be summarized using the Safety Set in Extension Phase. The following summaries will be provided:

- Number (%) of patients who are still on-treatment in Extension Phase (based on the 'End of Extension Treatment Phase' page not completed);
- Number (%) of patients who discontinued the Extension study treatment phase (based on the 'End of Extension Treatment Phase' page)
- Primary reason for Extension study treatment phase discontinuation (based on the 'End of Extension Treatment Phase' page)

Protocol deviations

The number (%) of patients in the FAS with any protocol deviation will be tabulated by deviation category (as specified in the study Data Handling Plan) and by cohort. Protocol deviations leading to exclusion from analysis sets will be tabulated separately by cohort. All protocol deviations will be listed.

Additional protocol deviation summaries will be provided to address the potential impact of COVID-19 pandemic in each cohort. The number and percentage of patients in the FAS with any protocol deviation with one of the following relationships will be summarized by deviation category: COVID-19 health status related, COVID-19 situation: Site issue, COVID-19 situation: Lockdown / Quarantine of patient, COVID-19 situation: Patient concern, COVID-19 situation: Drug supply issue and COVID-19 situation: Other.

Analysis sets

The number (%) of patients in each analysis set (defined in [Section 2.3](#)) will be summarized by cohort.

2.4 Treatments (study treatment, rescue medication, concomitant therapies, compliance)

2.4.1 Study treatment / compliance

Duration of exposure, actual cumulative dose, dose intensity (DI) and relative dose intensity (RDI) will be summarized by cohort, separately for each component of study treatment. Duration of exposure will be categorized into time intervals; frequency counts and percentages will be presented for the number (%) of patients in each interval. The number (%) of patients who have dose reductions, interruptions or permanent discontinuations, and the reasons, will be summarized by cohort.

Patient level listings of all doses administered on treatment along with dose change reasons will be produced.

The safety set will be used for all summaries and listings of study treatment in Core Phase.

The safety set in Extension Phase will be used for all summaries and listings of study treatment for the patients who enter the Extension Phase.

Duration of exposure to study treatment

Duration of exposure to study treatment is considered by taking into account the duration of exposure to the investigational drug (alpelisib) and any combination partner, if applicable:

Duration of exposure to study treatment (days) = (last date of exposure to study treatment) – (date of first administration of study treatment) + 1.

The last date of exposure to study treatment is the latest of the last dates of exposure to investigational drug or any combination partner (refer to [Section 2.1.1](#)).

Summary of duration of exposure of study treatment in appropriate time units will include categorical summaries (<2 months, 2-<4 months, 4-<6 months etc.) and continuous summaries (i.e. mean, standard deviation etc.) using appropriate units of time.

Duration of exposure to investigational drug and combination partner

Duration of exposure to investigational drug (days) = (last date of exposure to investigational drug) – (date of first administration of investigational drug) + 1.

Duration of exposure to fulvestrant (days) = (last date of exposure to fulvestrant) – (date of first administration of fulvestrant) + 1.

Duration of exposure to letrozole (days) = (last date of exposure to letrozole) – (date of first administration of letrozole) + 1.

Duration of exposure to goserilin (days) = (last date of exposure to goserilin) – (date of first administration of goserilin) + 1.

Duration of exposure to leuprolide (days) = (last date of exposure to leuprolide) – (date of first administration of leuprolide) + 1.

The definition of last date of study drug exposure is defined in [Section 2.1.1](#).

Summary of duration of exposure of investigational drug (alpelisib) will include categorical summaries based on monthly intervals (<2 months, 2-<4 months, 4-<6 months etc.) and using descriptive statistics (mean, standard deviation etc).

Cumulative dose

Cumulative dose of a study treatment is defined as the total dose given during the study treatment exposure and will be summarized for each of the study treatment components.

The **planned cumulative dose** for a study treatment component refers to the total planned dose as per the protocol up to the last date of investigational drug administration.

The planned cumulative dose is not summarized/listed. It is used for relative dose intensity calculations.

The **actual cumulative dose** refers to the total actual dose administered, over the duration for which the patient is on the study treatment as documented in the Dose Administration eCRF.

For patients who did not take any drug the cumulative dose is by definition equal to zero.

For continuous dosing, the actual cumulative dose is the sum of the non-zero doses recorded over the dosing period and the planned cumulative dose is the planned starting dose summed over the same dosing period.

For intermittent dosing, the actual cumulative dose should be defined based on the days when the patient is assumed to have taken a non-zero dose during dosing periods.

Dose intensity and relative dose intensity

Dose intensity (DI) for patients with non-zero duration of exposure is defined as follows:

DI (dosing unit / unit of time) = Actual Cumulative dose (dosing unit) / Duration of exposure to study treatment (unit of time).

For patients who did not take any drug the DI is by definition equal to zero.

Planned dose intensity (PDI) is defined as follows:

PDI (dosing unit / unit of time) = Planned Cumulative dose (dosing unit) / Duration of exposure (unit of time).

Relative dose intensity (RDI) is defined as follows:

RDI = DI (dosing unit / unit of time) / PDI (dosing unit / unit of time).

In this study DI, PDI and Relative dose intensity (RDI) are defined here below for the each study drugs.

Alpelisib:

- DI (mg/day) = Cumulative dose (mg) / duration of exposure (days)
- PDI is 300 mg/day
- RDI (%) = DI (mg/day) / PDI (mg/day) *100

Letrozole:

- DI (mg/day) = Cumulative dose (mg) / duration of exposure (days)
- PDI is 2.5 mg/day
- RDI (%) = DI (mg/day) / PDI (mg/day) *100

Fulvestrant, goserilin or leuprolide:

- DI (mg/day) = Cumulative dose (mg) / duration of exposure (days)

DI and RDI will be summarized separately for each of the study treatment components, but using the duration of exposure of each of the components.

Dose reductions, interruptions or permanent discontinuations

The number of patients who have dose reductions, permanent discontinuations or interruptions, and the reasons, will be summarized separately for each of the study treatment components.

‘Dose changed’, ‘Dose interrupted’, and ‘Dose permanently discontinued’ fields from the Dosage Administration CRF pages (DAR) will be used to determine the dose reductions, dose interruptions, and permanent discontinuations, respectively.

The corresponding fields ‘Reason for dose change/dose interrupted’ and ‘Reason for permanent discontinuation’ will be used to summarize the reasons.

A dose change is either ‘change in prescribed dose level’ or ‘dosing error’ where actual dose administered/total daily dose is different from the prescribed dose.

For the purpose of summarizing interruptions and reasons, in case multiple entries for interruption that are entered on consecutive days with different reasons will be counted as separate interruptions. However, if the reason is the same in this mentioned multiple entries on consecutive days, then it will be counted as one interruption.

The last zero dose of alpelisib/placebo or fulvestrant is not considered as a dose interruption.

Reduction: A dose change where the prescribed dose level is lower than the previous prescribed dose level or where the actual dose administered/total daily dose is lower than the calculated dose amount based on the prescribed dose. Therefore any dose change to correct a dosing error will not be considered a dose reduction. Only dose change is collected in the CRF, number of reductions will be derived programmatically based on the change and the direction of the change.

For alpelisib, a dose reduction is defined as a decrease in dose from the protocol planned starting dose (e.g. from 300 mg daily to 250 mg daily) even if the dose decrease has been directly preceded by an interruption. On the other hand, if the dose decrease is followed by an interruption, with the dose resuming at the same level prior to the interruption (e.g. in the sequence 300 mg daily – 0 mg - 300 mg daily), the second dose decrease or change in dosing frequency will not be counted as dose reduction.

If, due to a dosing error, a patient receives a higher than planned starting dose and moves down to the planned starting dose then this is not considered a dose reduction. However if the dose change is from a higher than planned starting dose down to a lower than protocol planned starting dose, then this is considered a dose reduction (e.g. in the sequence: 350 mg daily, 300 mg daily, 250 mg daily; 250 mg is considered a dose reduction in the case of alpelisib).

If, due to a dosing error, a patient receives a lower than previous non-zero dose and resumes later at the protocol specified dose reduction, then the lower dose received due to dosing error and protocol specified dose reduction are dose reductions (e.g. in the sequence 300 mg daily – 200 mg daily - 250 mg daily, then 200 mg and 250 mg are considered dose reductions).

If, due to a dosing error, a patient receives a lower than previous non-zero dose and resumes later at a lower than previous non-zero dose, then 2 dose reductions will be counted (e.g. in the sequence 300 mg daily - 250 mg daily – 200 mg daily, 250 mg and 200 mg are dose reductions).

Table 2-3 Examples of Dose Reduction for alpelisib

Sequence	Reduction
With dose change	
300 mg daily - 250 mg daily – 0 mg - 250 mg daily	1 reduction (the 1 st 250 mg)
300 mg daily – 300 mg daily – 0 mg - 250 mg daily	1 reduction (250 mg)
300 mg daily – 0 mg – 250 mg daily	1 reduction (250 mg)
With interruption	
300 mg daily – 0 mg - 300 mg daily	0 reductions
With dosing error	
300 mg daily – 250 mg daily – 200 mg daily*	2 reductions (250 mg, 200 mg)
300 mg daily – 200 mg daily* - 300 mg daily	1 reduction (200 mg)
300 mg daily – 200 mg daily* - 250 mg daily	2 reductions (200 mg, 250 mg)
300 mg daily – 400 mg daily* - 350 mg daily*	0 reductions since 400 mg and 350 mg are dose escalations not reduction
300 mg daily – 150 mg daily* - 300 mg daily	1 reduction (150 mg)
With dosing error at the 1st administration	
150 mg daily* - 300 mg daily	1 reduction (150 mg)

Sequence	Reduction
150 mg daily* - 0 mg - 150 mg*- 300 mg daily	1 reduction (150 mg)
150 mg daily* - 300 mg daily - 0 mg - 250 mg daily	2 reductions (150 mg and 250 mg)

*dosing error

There is no planned dose reduction for letrozole and fulvestrant; in addition the reason for fulvestrant dose reduction is not collected in the eCRF. No analysis for fulvestrant will be done on the number of, and reasons for, reductions. The established clinical dose of goserelin or leuprolide will be used in men and premenopausal women patients and no dose modification is planned in this study.

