6.1.4 Guidelines for continuation of treatment

For guidelines for continuation of treatment, refer to Section 6.3 Dosing modifications.

Patients who permanently discontinue one of the study drugs for any reason other than disease progression may continue the other study drug as part of the trial therapy at the investigator's discretion until disease progression, unacceptable toxicity, death or discontinuation from study treatment due to any other reason and should follow the protocol safety and efficacy assessments as scheduled. After discontinuing all study treatment, further treatment is left to the physician's discretion.

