2.1.1 General definitions

Investigational drug and study treatment

Investigational drug, will refer to the alpelisib (BYL719) only. Whereas, **study treatment** will refer to the combination drugs and includes investigational drug (alpelisib) as well as fulvestrant or letrozole and for men (cohort B) and premenopausal women goserelin or leuprolide as applicable in each of the study cohorts. Cohorts A and C include alpelisib/fulvestrant and cohort B includes alpelisib/letrozole.

The term investigational treatment may also be referred to as **study treatment** which is used throughout this document.

The term study drug can be used to refer to investigational and components of study treatment (fulvestrant or letrozole alpelisib and for men (cohort B) and premenopausal women goserelin or leuprolide as applicable).

Date of first administration of investigational drug

The date of first administration of investigational drug is defined as the first date when a non-zero dose of investigational drug is administered and recorded on the Dosage Administration Record (DAR) Electronic Case Report Form (eCRF) . The date of first administration of study drug will also be referred as start of investigational drug.

Date of last administration of investigational drug

The date of last administration of investigational drug is defined as is the last date when a nonzero dose of investigational drug is administered and recorded on DAR eCRF. The date of last administration of investigational drug will also be referred as end of investigational drug.

Date of first administration of study treatment

The date of first administration of study treatment is derived as the first date when a nonzero dose of any component of study treatment (alpelisib or letrozole/fulvestrant or goserelin/leuprolide for men (cohort B) and premenopausal women as applicable) was administered as per the Dosage Administration (e)CRF. Example: if 1st dose of alpelisib is administered on 05-Jan-2015, and 1st dose of fulvestrant is administered on 03-Jan-2015, then the date of first administration of study treatment is on 03-Jan-2015.

The date of first administration of study treatment will also be referred as *start of study treatment*.

Date of last administration of study treatment

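### Planned dose for relative dose intensity is tied to the last alpelisib date, so the figure promised for fulvestrant, goserelin and leuprolide is wrong when a scheduled injection falls between the two stop dates

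*SAP*

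**What the plan says.** All SAP references are to Amendment 4 (24-Mar-2022).

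Section 2.4.1, under cumulative dose, gives one general rule for what counts as planned, whichever drug is meant: it "refers to the total planned dose as per the protocol up to the last date of investigational drug administration". It is not tabulated itself; "It is used for relative dose intensity calculations". Section 2.1.1 says that investigational drug "will refer to the alpelisib (BYL719) only". The actual cumulative dose has no alpelisib cut-off.

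Two provisions then narrow the general rule:

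- For continuous dosing, "the planned cumulative dose is the planned starting dose summed over the same dosing period" as the actual dose.
- In the drug-by-drug list, alpelisib and letrozole have fixed planned dose intensities of 300 and 2.5 mg/day.

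For intermittent dosing, only the actual dose is described. The entry for fulvestrant, goserelin and leuprolide gives dose intensity (DI) alone, with no planned dose intensity (PDI) and no RDI. Even so, the section opens by announcing RDI for each component, and closes with "DI and RDI will be summarized separately for each of the study treatment components", on each component's own duration of exposure.

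Protocol 6.1.4 lets the drugs stop at different times: a patient who permanently stops one study drug for a reason other than progression "may continue the other study drug as part of the trial therapy".

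**The concern.** RDI should compare what was given with what was planned over one period. For the three injectables, the numerator runs over the drug's own period and the only available denominator runs to the last alpelisib day. A patient who stops alpelisib for toxicity and stays on fulvestrant can show an RDI far above 100%. A patient who stops fulvestrant first can show one far below it. A real missed injection can be hidden inside an inflated figure.

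At stake is the description of partner-drug delivery, chiefly fulvestrant in Cohorts A and C. RDI is also listed among the outputs of the first two interim analyses (SAP 2.14).

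**Working it through.** **Inputs.** Fulvestrant is scheduled at 500 mg on Days 1, 15, 29 and every 28 days after that (Protocol 6.1.1.3). Goserelin 3.6 mg and leuprolide 7.5 mg are scheduled every 28 days from Day 1 (Protocol 6.1.1.4 and 6.1.1.5). The stop dates below are assumptions; the documents give none.

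**Step 1: the SAP's own figures.** Summed over each drug's own dosing period, PDI is 300 mg/day for alpelisib and 2.5 mg/day for letrozole, as stated. The alpelisib cut-off applied literally to letrozole would not give 2.5. With alpelisib for 84 days and letrozole for 168, it gives 84 × 2.5 / 168 = 1.25 mg/day. With the durations swapped, it gives 168 × 2.5 / 84 = 5.0. The fixed value therefore overrides the general sentence, and letrozole is safe.

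**Step 2: the formula for the injectables.** The general formulas are DI = actual cumulative dose / duration, PDI = planned cumulative dose / duration, and RDI = DI / PDI. With the component's own duration in both, the duration cancels and RDI = actual / planned cumulative dose. The own-duration clause therefore does not repair a planned dose that ends on the wrong day.

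**Step 3: two cases for fulvestrant, with every scheduled injection given until the drug is stopped.**

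- Alpelisib to Day 84, fulvestrant to Cycle 9 Day 1 (Day 225). Given: Days 1, 15, 29, 57, 85, 113, 141, 169, 197, 225 = 10 × 500 = 5000 mg. Planned to Day 84: Days 1, 15, 29, 57 = 2000 mg. RDI = 5000/2000 = 250%.
- Fulvestrant stopped after Cycle 2 Day 1 (Day 29), alpelisib to Day 225. Given: 3 × 500 = 1500 mg. Planned to Day 225: 5000 mg. RDI = 1500/5000 = 30%.

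Counted to the end of fulvestrant exposure, both are 100%.

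**Step 4: other assumed dates, again with full compliance.**

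| Drug, last injection | Given | Last alpelisib day | Planned by the rule | RDI by the rule |
|---|---|---|---|---|
| Fulvestrant, Day 309 | 6500 mg | 336 | 6500 mg | 100% |
| Fulvestrant, Day 309 | 6500 mg | 168 | 3500 mg | 185.7% |
| Fulvestrant, Day 309 | 6500 mg | 84 | 2000 mg | 325% |
| Fulvestrant, Day 57 | 2000 mg | 168 | 3500 mg | 57.1% |
| Goserelin, Day 309 | 43.2 mg | 84 | 10.8 mg | 400% |
| Goserelin, Day 57 | 10.8 mg | 168 | 21.6 mg | 50% |

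Leuprolide gives the same percentages as goserelin (90.0/22.5 = 400%; 22.5/45.0 = 50%).

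**Step 5: where the error begins.** Take fulvestrant last given on Day 85 (5 injections, 2500 mg). With alpelisib to Day 100 or Day 112, planned is 2500 mg and RDI is correctly 100%. With alpelisib to Day 113, planned is 3000 mg and RDI is 83.3%. With alpelisib to Day 84, planned is 2000 mg and RDI is 125%. The error needs a scheduled injection after the earlier stop and on or before the later one.

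**Step 6: masking.** If one of 13 fulvestrant injections is missed (6000 mg given), RDI should be 6000/6500 = 92.3%. With alpelisib stopped on Day 84, the rule gives 6000/2000 = 300%.

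**Step 7: no alpelisib date.** The safety set (SAP 2.2) requires one dose of any component. A patient who never took alpelisib has no cut-off date, so the planned dose and RDI are undefined.

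**The case against.** The best defence is that the SAP never applies the general formula to the injectables. Its drug-by-drug list is introduced as the definitions for this study, and for these three drugs it stops at DI. On that reading no RDI is computed and no 250% ever appears. Intent to work per component is also visible: each drug has its own duration, and the cut-off wording may be a slip.

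Part of this stands. The defect can be read as a missing definition. But RDI for each component is promised twice, and an analyst who keeps that promise finds only one planned-dose rule, which gives the wrong figure.

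It also stands that little depends on RDI. It enters no efficacy endpoint and no listed per-protocol exclusion. Duration, actual cumulative dose, DI, dose listings, interruptions and discontinuations still show partner exposure. Protocol 10.3 commits to dose intensity, not to RDI.

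A reader might infer more than the documents support:

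- *Every component is affected.* The general sentence is worded that way, but the continuous-dosing rule and the fixed PDIs protect alpelisib and letrozole.
- *Any difference in stop dates corrupts RDI.* Step 5 shows that stops with no scheduled injection between them give the right value.
- *Fulvestrant DI is also defective because it falls over time at full compliance.* That follows from the extra Day 15 injection, and the SAP sets no constant target for DI.

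**Conclusion.** The planned-dose rule is wrong as written for fulvestrant, goserelin and leuprolide. It makes their planned dose too short when alpelisib stops first and too long when the injectable stops first. RDI is wrong whenever a scheduled injection falls between the two stops, and it is undefined without an alpelisib date. In the fully compliant examples above, affected values run from 30% to 400% where 100% is right.

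This rests on three things: the general formula is used to deliver the promised RDI, the component's own duration enters both DI and PDI, and the stop dates are illustrative. The share of patients affected is not stated. Protocol 6.4.1.1 reports that 18 of 284 patients (6%) in the earlier phase III study stopped alpelisib for hyperglycemia. This shows that alpelisib is stopped for toxicity, but not how many such patients continued fulvestrant, nor what to expect here.

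The consequence is confined to descriptive exposure summaries. The primary endpoint, sample size and efficacy analyses are untouched. The correction is worth making because the figure is promised and the change is small.

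**What to change.** In SAP 2.4.1, end the planned cumulative dose at each component's own last date of exposure, as already derived in 2.1.1. Add explicit PDI and RDI lines for the three injectables, with RDI = actual / planned cumulative dose and the planned dose counted from the protocol's injection schedule. Two details need a sentence each:

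- Patients already on goserelin or leuprolide keep their existing 28-day schedule (Protocol 6.1.1.4 and 6.1.1.5), so their planned injections should be anchored to it.
- Protocol 6.1.1 allows ±3 days around fulvestrant dosing. A Day 85 injection given on Day 88 ends exposure on Day 88 + 27 = 115, which takes in scheduled Day 113. Counting by cycle rather than by calendar day avoids charging a dose that was not yet due.

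Alternatively, state that RDI is not computed for these three drugs, remove the promise at the start and end of the section, and limit the RDI item in 2.14 to alpelisib and letrozole.

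Either route costs one SAP definition and, where RDI is kept, its program. No new data are needed.
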